5.6.2. Long-term Follow-up

Patients will be followed for survival and initiation of new anticancer therapy via telephone contact or other means (eg, clinic visit) approximately every 12 weeks ([Appendix 1](#)).

Patients who do not have objective disease progression at the time of pamiparib permanent discontinuation but meet other discontinuation criteria (eg, discontinued for AE and no new anticancer therapy) will continue to have tumor and PSA assessments every 12 weeks and 4 weeks (± 7 days), respectively, until PD or any other reason listed in [Section 5.6.4](#), whichever occurs first. For efficacy assessments as per protocol, refer to [Section 7.3](#) and [Appendix 1](#). If the patient refuses to return for these PSA and tumor assessments or is unable to do so, every effort should be made to contact the patient by telephone to determine the patient's disease status and survival.

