10.2. Efficacy Analyses

10.2.1. Primary Efficacy Endpoint Analyses

The primary endpoints of the study include ORR by IRC assessment in CTC-HRD-positive patients with measurable disease and PSA response rate in CTC-HRD-positive patients with or without measurable disease per PCWG3 criteria.

ORR is defined as the proportion of patients with best objective response of CR or PR confirmed at a subsequent timepoint ≥ 4 weeks later by IRC assessment. Patients without tumor assessment are considered non-responders.

ORR is assumed as 35% for pamiparib and estimated as 15% for historical control in the study population. The null and alternative hypotheses are set as follows:

$$H_0: \text{ORR} = 15\%$$

$$H_a: \text{ORR} > 15\%$$

PSA response rate is defined as the proportion of patients with PSA decline $\geq 50\%$ from baseline (confirmed by a second PSA value ≥ 3 weeks later).

PSA response rate is assumed as 50% for pamiparib and estimated as 30% for historical control in the study population. The null and alternative hypotheses are set as follows:

$$H_0 : \text{ORR} = 30\%$$

$$H_a : \text{ORR} > 30\%$$

Binomial exact tests will be performed for above hypotheses in the Efficacy-Evaluable Analysis Set. Two-sided binomial exact 95% CI of response rate will be constructed to assess the precision of the estimates.

To control the overall study type-I error rate, ORR and PSA response rate will be tested sequentially. If the ORR test shows significance at 1-sided 0.025 significance level, PSA response rate will be tested at a 1-sided 0.025 significance level.

The primary efficacy analyses will be conducted when mature response data have been observed, which will be determined by the sponsor.

A sensitivity analysis of response rate will be conducted using the Safety Analysis Set.

ORR and PSA response rate will be summarized in the specified subgroups: age group (< 65 versus ≥ 65), race, geographic region, ECOG performance status, BRCA1/2-mutant status, and number of prior lines of therapy.

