## 6 STATISTICAL METHODS

### 6.1 ANALYSIS POPULATIONS

- Safety Analysis Set (SAF): includes all patients enrolled in the study who receive any dose of pamiparib. The Safety Analysis Set will be used for all safety analyses.
- Efficacy-Evaluable Analysis Set (ORR Assessment in Cohort 1 of Table 1): includes all patients in the Safety Analysis Set who had measurable disease at baseline and at least 1 postbaseline tumor assessment, unless they permanently discontinue pamiparib or the study early due to clinical progression or death prior to tumor assessment. A similar analysis population will exist for exploratory analyses of Cohort 3.
- Efficacy-Evaluable Analysis Set (PSA Response Rate Assessment in Cohorts 1 and 2 of Table 1): includes all patients in the Safety Analysis Set as per Inclusion Criterion 7 at baseline ( $\geq 3$  rising PSA levels with  $\geq 1$  week between determinations and screening PSA  $\geq 2$   $\mu\text{g/L}$ ) and who had at least 1 postbaseline PSA measurement, unless they permanently discontinue pamiparib or the study early due to clinical progression or death before completed PSA assessment. A similar analysis population will exist for exploratory analyses of Cohorts 3 and 4.
- PK Analysis Set: includes all patients who received pamiparib and contributed at least one plasma concentration.

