### 6.2.3 Handling of Missing Data

Missing data will not be imputed unless otherwise specified elsewhere in the SAP. Missing dates or partially missing dates will be imputed conservatively for adverse events and prior/concomitant medications/procedures. Specific rules for handling of missing or partially missing dates for adverse events and prior/concomitant medications/procedures are provided in Appendix 10.1.

By-visit endpoints will be analyzed using observed data, unless otherwise specified. For observed data analyses, missing data will not be imputed and only the observed records will be included.

When summarizing categorical variables, patients with missing data are included in the denominator to calculate percentages unless otherwise specified. When needed, the category of “Missing” is created and the number of patients with missing data is presented.

When summarizing continuous variables, patients with missing data are not included in calculations. No imputations are made.

For the Health-related quality of life (HRQoL) questionnaires, the missing data will be handled in accordance with the scoring manual of each patient-reported outcome (PRO) questionnaire (Cleeland, 2009).

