#### PSA Response Rate

PSA response rate is defined as the proportion of patients with a PSA decline  $\geq 50\%$  from baseline confirmed by a second PSA value  $\geq 3$  weeks later. For this primary efficacy endpoint, the PSA assessments will be summarized for the Efficacy-Evaluable Analysis Set (PSA Response Rate Assessment in Cohorts 1 and 2).

PSA response rate (number and proportion of patients) will be presented along with its Clopper-Pearson 2-sided 95% confidence interval. The number and proportion of patients who achieve an unconfirmed PSA decline  $\geq 50\%$  from baseline will also be summarized.

If the primary efficacy endpoint of ORR is statistically significant, PSA response rate will be tested against a historical control PSA response rate, and the null and alternative hypotheses are as follows:

$H_0$ : PSA response rate = 30%

$H_a$ : PSA response rate > 30%

A binomial exact test will be performed for the above hypotheses at a one-sided 0.025 significance level. If the result for PSA response rate is statistically significant, ie, one-sided p-value < 0.025, then PSA response rate will be considered statistically significant. Note that if the primary efficacy endpoint of ORR is not statistically significant, then no claims of statistical significance can be made for the primary efficacy endpoint of PSA response rate.

If the Efficacy-Evaluable Analysis Set (PSA Response Rate Assessment in Cohorts 1 and 2) is not equivalent to the Safety Analysis Set for Cohorts 1 and 2, a sensitivity analysis of PSA response rate will be conducted on the Safety Analysis Set for Cohorts 1 and 2. The sensitivity analysis will be carried out in the Safety Analysis Set. Patients without postbaseline tumor assessment will be considered as non-responders in the Safety Analysis Set and will be classified as “not assessed.”

Subgroup analyses for PSA response rate will be performed as described in Section [6.4.3](#).

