#### 8 CHANGES IN THE PLANNED ANALYSIS

Due to upcoming changes in standard of care, changes in program strategy, slow enrolment and apparent lack of responses, the trial was terminated after enrolling 13 patients in cohort 1B and cohort 2B. The final clinical study report will not include all the planned analyses per protocol including the interim analysis because the milestone of enrolling 20 patients was not reached. For the final clinical study report, tables of patient disposition and reasons for discontinuation, demographics and baseline characteristics and prior anti-cancer therapies will be provided. No efficacy related tables or analysis will be conducted. Tumor assessment result by investigator (target lesions by time point and bone lesions) will be listed but result by IRC will not be

included in the final clinical study report, because of the small number of patients enrolled and the fact that the majority of the patients did not had postbaseline tumor assessments. HRQoL data results will be listed. Data from PSA assessments will be provided in listings and discussed in the clinical study report. Exposure data, safety analyses and PK analyses will be conducted as planned. ECOG performance shift table will not be conducted. The biomarker data will be provided as listings.

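### The PSA sensitivity analysis in SAP 6.4.1 repeats the ORR rule, so non-response is assigned for a missing tumor scan instead of a missing PSA value

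*SAP*

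**What the plan says.** SAP 6.4.1, under PSA Response Rate, defines response as a PSA decline of at least 50% from baseline, confirmed by a second PSA value at least 3 weeks later. The primary population is the PSA evaluable set of SAP 6.1. It requires patients "who had at least 1 postbaseline PSA measurement", with an exception for early discontinuation because of clinical progression or death.

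If that set differs from the Safety Analysis Set, "a sensitivity analysis of PSA response rate will be conducted on the Safety Analysis Set for Cohorts 1 and 2". The classification rule for that analysis is: "Patients without postbaseline tumor assessment will be considered as non-responders in the Safety Analysis Set". These patients also receive the label *not assessed*. The same sentence stands in the ORR part of 6.4.1.

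Protocol 10.2.1 has a related rule, "Patients without tumor assessment are considered non-responders", placed directly after the ORR definition. The protocol's own sentence on the Safety Analysis Set sensitivity analysis gives no scan-based rule for PSA.

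**The concern.** The rule uses the wrong assessment for this endpoint. Whether a patient has a PSA response depends on PSA values; whether he was scanned has no bearing on it. As written, a confirmed PSA responder without a postbaseline scan becomes a non-responder labelled *not assessed*, although his PSA was assessed at least twice after baseline. A patient with no postbaseline PSA gets no such label unless he also lacks a scan.

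The sensitivity analysis is meant to show whether the PSA result depends on leaving out patients without PSA data. A confirmed responder necessarily has postbaseline PSA. So, apart from patients who miss Inclusion Criterion 7, moving to the Safety Analysis Set should add only non-responders: the denominator grows and the numerator stays. Under the written rule the numerator can fall as well. A gap between the primary and sensitivity results could then reflect missing scans and not the choice of analysis set.

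**Working it through.** **1. The texts side by side**

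| Place | Endpoint | What the rule depends on |
|---|---|---|
| SAP 6.1, PSA evaluable set | PSA response | postbaseline PSA |
| SAP 6.4.1, PSA response definition | PSA response | PSA decline and confirming PSA |
| Protocol 10.2.1, ORR definition | ORR | tumor assessment |
| SAP 6.4.1, ORR sensitivity analysis | ORR | tumor assessment |
| SAP 6.4.1, PSA sensitivity analysis | PSA response | **tumor assessment** |

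Only the last row departs from its own endpoint. Patients with no PSA value cannot meet the response definition, and SAP 6.2.3 keeps them in the denominator: "patients with missing data are included in the denominator to calculate percentages unless otherwise specified". The numerical error is therefore confined to confirmed PSA responders who have no postbaseline scan.

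**2. Reproducing the planned figures**

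Inputs from SAP Section 5: n = 80, null rate 30%, assumed rate 50%, one-sided 0.025, exact binomial test.

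- Critical value, the smallest r with P(X ≥ r | 80, 0.30) < 0.025: P(X ≥ 32) = 0.0360 and P(X ≥ 33) = 0.0211, so r = 33.
- Power: P(X ≥ 33 | 80, 0.50) = 0.954, against the stated 95%.
- Exact interval for x of n: lower limit is the 0.025 quantile of Beta(x, n − x + 1), upper limit the 0.975 quantile of Beta(x + 1, n − x). For 40/80 this gives 38.6% to 61.4%, as stated.

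The design figures are correct.

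**3. Effect of the rule as written**

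The documents do not say how many PSA responders would have no postbaseline scan, so this number is an assumption, shown as a range. Take 40 true responders in 80 (50%) and let m of them be unscanned. The counted rate is (40 − m)/80, a loss of 1/80 = 1.25 points per patient.

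| m (share of 40) | Counted | Rate | Exact 95% CI | One-sided p against 30% |
|---|---|---|---|---|
| 0 (0%) | 40/80 | 50.0% | 38.60% to 61.40% | 0.0001 |
| 2 (5%) | 38/80 | 47.5% | 36.21% to 58.98% | 0.0007 |
| 4 (10%) | 36/80 | 45.0% | 33.85% to 56.53% | 0.0032 |
| 7 (17.5%) | 33/80 | 41.25% | 30.35% to 52.82% | 0.0211 |
| 8 (20%) | 32/80 | 40.0% | 29.20% to 51.56% | 0.0360 |

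The lower limit first falls below 30% at m = 40 − 32 = 8. With the rule tied to PSA, the planned case stays at 40/80 for every m.

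**4. Can such a patient occur?**

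PSA is due on Day 1 and every 4 weeks; scans are first due at week 8 (± 7 days). A decline seen at Day 29 can be confirmed from Day 29 + 21 = Day 50. The next scheduled PSA is at Day 57, about when the first scan is due. An unscheduled PSA, the visit windows or missed imaging could leave a confirmed responder unscanned. For patients who stop without progression, Protocol 5.6.2 says they "will continue to have tumor and PSA assessments every 12 weeks and 4 weeks", and scans are also due at End of Treatment. So the group is possible, but should be small in a full trial.

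**The case against.** The strongest objection is that nothing reported depends on this sentence. SAP Section 8 says the trial stopped after 13 patients and that "No efficacy related tables or analysis will be conducted"; PSA data go to listings. Even as planned, the analysis runs only if the two sets differ, and it carries no alpha. The primary PSA definition, population, test and place in the testing sequence all rest on PSA. The error is conservative, so it cannot create a false claim of efficacy. All of this stands and is why the point is minor.

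On schedule, PSA confirmation coincides roughly with the first scan, and later scans follow. An affected patient must have missed the week 8 imaging and every later scan. This also stands: the 20% row marks a tipping point and is not an expected effect. At 5% and 10% the interval still excludes 30%.

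It can also be said that the scan condition adds to the PSA criterion and does not replace it, because patients without PSA data are non-responders anyway. That is right for the count. The written classification rule nevertheless refers to scans and does not mention PSA.

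Section 8 reports that most enrolled patients had no postbaseline tumor assessment, which shows that missing scans did occur here. It does not raise the stakes: the same section reports an apparent lack of responses, and nothing shows that any PSA responder would have been reclassified.

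**Conclusion.** The concern holds as a minor one. The rule in the PSA paragraph is wrong as written: it would count a confirmed PSA responder as a failure because of a missing scan, and nothing in either document supports a scan requirement for PSA response.

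Any bias is downward and limited to a conditional sensitivity analysis. The tipping point of 8 unscanned responders rests on the planning assumption of 40 responders in 80; the unscanned share is an assumption throughout, with no effect at zero. Confidence is high because the finding rests on the text. The correction concerns the planned analysis and any later reuse of it.

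**What to change.** In SAP 6.4.1, PSA Response Rate, replace the word *tumor* with *PSA* in the sentence on non-responders in the Safety Analysis Set. Patients without a postbaseline PSA assessment are then the ones classed as non-responders and labelled *not assessed*. This agrees with the evaluability criterion in SAP 6.1. Scan status should play no part in the PSA analysis. The ORR sentence stays as it is.

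The cost is one word in the SAP and the matching line in any programming specification that follows it. Alpha, sample size, the primary analysis and the final report are unchanged.

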## 6.4.2 Secondary Efficacy Endpoints

### Duration of Response (DOR) by IRC

DOR is defined as the time from the date of the earliest documented CR or PR (that is subsequently confirmed) to radiographic disease progression or death due to any cause, whichever occurs first. The censoring rules for DOR will be similar to those for rPFS described in Appendix 10.2 except that the situation of “No baseline tumor assessments” will not apply to DOR. For this secondary efficacy endpoint, the tumor assessments will be performed by the IRC and will be summarized for patients in the Efficacy-Evaluable Analysis Set (ORR Assessment in Cohort 1) who have achieved a confirmed objective response.

DOR will be estimated using the Kaplan-Meier method, and the median DOR will be presented along with its 2-sided 95% confidence interval using the Brookmeyer and Crowley method (Brookmeyer and Crowley 1982). The event-free rate at select timepoints will be calculated along with 2-sided 95% confidence intervals using Greenwood’s formula.

### ORR by Investigator (INV)

ORR is defined as for the primary efficacy endpoint. For this secondary efficacy endpoint, the tumor assessments will be performed by the investigator and will be summarized for the Efficacy-Evaluable Analysis Set (ORR Assessment in Cohort 1).

ORR (number and proportion of patients) will be presented along with its Clopper-Pearson 2-sided 95% confidence interval. The number and proportion of patients who achieve an unconfirmed best objective response of CR or PR will also be summarized.

#### Time to Objective Response by INV

Time to objective response is defined as the time from the date of the first dose of study drug to the first documented confirmed response of CR or PR. For this secondary efficacy endpoint, the tumor assessments will be performed by the investigator and will be summarized for patients in the Efficacy-Evaluable Analysis Set (ORR Assessment in Cohort 1) who have achieved a confirmed objective response.

Time to objective response will be presented using descriptive statistics (e.g., n, mean, standard deviation, median, Q1, Q3, minimum, maximum).

#### Clinical Benefit Rate by INV

Clinical benefit rate is defined as the proportion of patients with a documented confirmed CR, PR or SD. For this secondary efficacy endpoint, the tumor assessments will be performed by the investigator and will be summarized for the Efficacy-Evaluable Analysis Set (ORR Assessment in Cohort 1).

The clinical benefit rate (number and proportion of patients) will be presented along with its Clopper-Pearson 2-sided 95% confidence interval.

#### Time to PSA Response

Time to PSA response is defined as the time from the date of the first dose of study drug to the first PSA decline  $\geq 50\%$  that is subsequently confirmed. For this secondary efficacy endpoint, the PSA assessments will be summarized for patients in the Efficacy-Evaluable Analysis Set (PSA Response Rate Assessment in Cohorts 1 and 2) who have achieved a confirmed PSA response.

Time to PSA response will be presented using descriptive statistics (e.g., n, mean, standard deviation, median, Q1, Q3, minimum, maximum).

#### Duration of PSA Response

Duration of PSA response is defined as the time from the date of the earliest documented PSA response (that is subsequently confirmed) to PSA progression or death due to any cause, whichever occurs first. PSA progression is defined as a  $\geq 25\%$  increase in PSA with an absolute increase of  $\geq 2 \mu\text{g/L}$  above the nadir (or above the baseline for patients with no PSA decline after 12 weeks), confirmed by a second value  $\geq 3$  weeks later. The nadir is defined as the lowest value at or after baseline. For patients who have not died or had a PSA progression event as of the data cutoff date, duration of PSA response will be censored at the date of the last PSA assessment. The PSA assessments will be summarized for patients in the Efficacy-Evaluable Analysis Set

(PSA Response Rate Assessment in Cohorts 1 and 2) who have achieved a confirmed PSA response.

Duration of PSA response will be estimated using the Kaplan-Meier method, and the median duration of PSA response will be presented along with its 2-sided 95% confidence interval using the Brookmeyer and Crowley method. The event-free rate at select timepoints will be calculated along with 2-sided 95% confidence intervals using Greenwood's formula.

#### Time to PSA Progression

Time to PSA progression is defined as the time from the date of the first dose of study drug to the date of a  $\geq 25\%$  increase in PSA with an absolute increase of  $\geq 2$   $\mu\text{g/L}$  above the nadir (or above the baseline for patients with no PSA decline after 12 weeks), confirmed by a second value  $\geq 3$  weeks later. For patients who have not had a PSA progression event as of the data cutoff date, time to PSA progression will be censored at the date of the last PSA assessment. For this secondary efficacy endpoint, the PSA assessments will be summarized for the Safety Analysis Set (Cohorts 1 and 2).

Time to PSA progression will be estimated using the Kaplan-Meier method, and the median time to PSA progression will be presented along with its 2-sided 95% confidence interval using the Brookmeyer and Crowley method. The event-free rate at select timepoints will be calculated along with 2-sided 95% confidence intervals using Greenwood's formula.

#### Time to Symptomatic Skeletal Event (SSE)

Time to SSE is defined as the time from the date of the first dose of study drug to the date of the first symptomatic fracture, radiation or surgery to bone or spinal cord compression. For patients who have not had an SSE as of the data cutoff date, time to SSE will be censored at the date of the last visit. This secondary efficacy endpoint will be summarized for the Safety Analysis Set (Cohorts 1 and 2).

Time to SSE will be estimated using the Kaplan-Meier method, and the median time to SSE will be presented along with its 2-sided 95% confidence interval using the Brookmeyer and Crowley method. The event-free rate at select timepoints will be calculated along with 2-sided 95% confidence intervals using Greenwood's formula.

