9.3. Timing, Frequency, and Method of Capturing Adverse Events and Serious Adverse Events

9.3.1. Adverse Event Reporting Period

After the ICF has been signed, but before initiation of pamiparib, only SAEs should be reported to the sponsor.

After initiation of treatment, all AEs and SAEs, regardless of relationship to treatment, will be reported until 30 days after the last dose of pamiparib or initiation of new anticancer therapy, whichever occurs first. After this period, the investigator should report any SAEs that are believed to be related to prior study drug treatment.

After a patient is discontinued from the study, investigators are not obligated to actively seek AEs or SAEs from the former patients. However, if the investigator learns of any SAE, including a death, at any time, and considers the SAE related to pamiparib, the investigator will notify the sponsor.

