- l. Following the screening tumor assessment, tumor assessments will occur at the schedule of every 8 weeks (± 7 days) after Day 1 for the first 24 weeks, then at the schedule of every 12 weeks (± 7 days). Any measurable disease must be documented at screening and reassessed at each subsequent tumor evaluation. The same imaging method(s) used at screening must be used throughout the study. A documented standard-of-care tumor assessment may be used as the screening assessment provided it meets protocol requirements ([Section 7.3.1.2](#)). CT scan with intravenous contrast is the preferred imaging method for assessment of chest, abdomen, and pelvis. Other imaging methods are allowed as outlined in [Section 7.3.1.2](#). Imaging of other areas of disease should be performed every 8 weeks ± 7 days for 24 weeks, then every 12 weeks ± 7 days. Patients without PD at the EOT Visit should be followed with tumor

assessments every 12 weeks (± 7 days) during the long-term follow-up phase.

- m. Whole-body radionuclide bone scan must be performed at screening and will then occur at the schedule of every 8 weeks (± 7 days) after Day 1 for the first 24 weeks, then at the schedule of every 12 weeks (± 7 days). Patients without PD at the EOT Visit should be followed with bone scans every 12 weeks (± 7 days) during the long-term follow-up phase.
- n. MRI scan of the brain to assess for brain metastases must be performed at screening if the patient has symptoms that could be due to brain metastases. CT scan with intravenous contrast is acceptable if MRI is not available or the patient is claustrophobic. If brain metastases are present at baseline, the patient is eligible for this study if criteria listed under Exclusion Criterion 8 are met.
- o. AEs and laboratory safety measurements will be recorded at each study visit, graded per National Cancer Institute-Common Terminology Criteria for Adverse Events Version 4.03 or higher, and assessed as outlined in [Section 9](#). After the informed consent form has been signed, but before initiation of pamiparib, only SAEs should be reported. After initiation of pamiparib, all AEs and SAEs, regardless of relationship to pamiparib, will be reported until 30 days after last dose of pamiparib or initiation of new anticancer therapy, whichever occurs first. After this period, the investigator should report any SAEs that are believed to be related to pamiparib.

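### Time to SSE is censored at an undefined last visit that is not tied to SSE ascertainment, so time in which disease-related SSEs are largely not captured can count as event-free

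*SAP*

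**What the plan says.** SAP 6.4.2 defines the event as "the first symptomatic fracture, radiation or surgery to bone or spinal cord compression" and analyses it by Kaplan-Meier in the treated patients of Cohorts 1 and 2. Patients without an event are handled by one rule: "time to SSE will be censored at the date of the last visit". The term is not defined.

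On collection, the Protocol says the following.

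- Appendix 1 has no SSE row. Section 7.3 covers tumor, PSA, survival and quality-of-life assessments.
- Under Section 9.3.1, all adverse events, whatever their cause, "will be reported until 30 days after the last dose of pamiparib or initiation of new anticancer therapy, whichever occurs first". Then: "After this period, the investigator should report any SAEs that are believed to be related to prior study drug treatment".
- Appendix 1 marks the adverse event row in long-term follow-up, but its footnote sets the same limit: "After this period, the investigator should report any SAEs that are believed to be related to pamiparib".
- Section 5.6.2 describes long-term follow-up: "Patients will be followed for survival and initiation of new anticancer therapy via telephone contact or other means", about every 12 weeks. Patients who stop drug without progression also have PSA every 4 weeks and tumor assessments every 12 weeks until progression.
- Section 5.7 places the last patient's last visit at the end of long-term follow-up.

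**The concern.** A Kaplan-Meier estimate treats a patient as at risk and event-free up to the censoring date. That is valid only if an event before that date would have been recorded. Here SSEs surface indirectly, mainly as adverse events, and that route closes soon after the last dose unless the event is serious and judged drug-related. A pathological fracture or cord compression attributed to the cancer would usually not meet that test.

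If the last visit falls after the route closes, the interval between adds follow-up but almost no events. The event-free rate is then too high and the median too long. The effect is largest in patients who stop drug early and are followed for long afterwards.

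The SAP avoids this for its other assessed endpoints. Duration of PSA response and time to PSA progression are censored at the last PSA assessment, and rPFS at the last radiologic assessment. SSE has no matching rule.

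**Working it through.** **No plan figure to reproduce.** Neither document gives an SSE rate, event count or precision.

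**Step 1: which visits fall after collection ends?**

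- *Patients off drug without progression.* PSA and scan visits continue beyond the adverse event window (Protocol 5.6.2). These are visits on any reading, and neither PSA nor a bone scan establishes a symptomatic event.
- *Patients off drug with progression.* The last scheduled clinic visit is the Safety Follow-up Visit at about 30 days (Protocol 5.6.1). After that only the 12-weekly survival contact is required, which may be by telephone. Whether it counts as a visit is not stated.

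**Step 2: a version that can be checked by hand.** Assume exponential times, no deaths, everyone followed to 12 months, and SSEs recorded only to 1 month after the last dose. With SSE hazard λ and treatment-stopping hazard μ per month, the recorded 12-month incidence is

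P = (1 − e^(−λ)) + e^(−λ) × λ/(λ+μ) × (1 − e^(−11(λ+μ))).

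- Assumed SSE median of 12 months: λ = ln 2/12 = 0.0578, so true incidence is 50%.
- Treatment median of 4 months: μ = 0.1733 and P = 0.0561 + 0.9439 × 0.25 × 0.9213 = 0.274, about 27%.
- Treatment median of 6 months: μ = 0.1155 and P = 0.0561 + 0.9439 × 0.3333 × 0.8513 = 0.324, about 32%.

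**Step 3: simulation with deaths and staggered follow-up.** There were 400,000 patients per scenario with independent exponential times. Inputs:

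- Median time on drug 2.7 or 9.8 months, paired with median OS 7.5 or 13.8 months. These are the rPFS and OS figures of the single-agent olaparib study cited in Protocol 1.3, used only as a range.
- Data cutoff uniform over 12 to 31 months; Protocol 3.4 gives a study duration of about 31 months.
- Contacts every 12 weeks after stopping drug.
- SSE median 9, 15 or 24 months (assumed). The true 12-month event-free rate is 0.5^(12/median).
- SSEs recorded only to 30 days after the last dose.

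12-month event-free rate, %:

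| SSE median (months) | Drug / OS median (months) | True | Censored at last contact | Excess (points) | Censored at end of collection |
|---|---|---|---|---|---|
| 9 | 2.7 / 7.5 | 39.7 | 70.9 | 31.2 | 39.7 |
| 9 | 9.8 / 13.8 | 39.7 | 53.2 | 13.5 | 39.7 |
| 15 | 2.7 / 7.5 | 57.4 | 80.8 | 23.4 | 57.8 |
| 15 | 9.8 / 13.8 | 57.4 | 67.7 | 10.3 | 57.4 |
| 24 | 2.7 / 7.5 | 70.7 | 87.3 | 16.6 | 70.8 |
| 24 | 9.8 / 13.8 | 70.7 | 78.1 | 7.4 | 70.6 |

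Across the scenarios, 34% to 57% of time up to the last contact falls after collection ends, and 25% to 53% of SSEs before that contact go unrecorded. The apparent hazard is 0.43 to 0.65 of the true one. Censoring at the end of collection restores it (ratio 1.00), given independence.

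**Step 4: limits of the simulation.** It assumes no capture after the window, which overstates the gap. It ignores the earlier stop of reporting at new anticancer therapy, which understates it. If SSE risk rises after progression, the gap would be larger. The case in which only the PSA and scan visits of non-progressing patients extend censoring was not simulated, because the documents do not say how many such patients to expect. It would lie between little and the figures above.

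**The case against.** The strongest objection is that last visit need not reach the survival contacts. The Protocol distinguishes telephone contacts from clinic visits, and the SAP had other wording available: OS is censored at data cutoff or the date last known alive. For a patient who progresses, the last visit may be the Safety Follow-up Visit, and the rule then nearly coincides with the end of collection. This stands in part. A reader might infer that the SAP plainly counts the 12-weekly contacts as event-free time. It does not say so. Section 5.7 points that way, but it defines the end of the study, not a patient's censoring date. The objection does not remove the PSA and scan visits of patients off drug without progression.

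A reader might also infer that no SSE can be recorded after the window. That is too strong. Drug-related serious events are still reported. New anticancer therapy is recorded throughout follow-up, so some bone radiation might appear there, although Protocol 6.2.2 treats radiotherapy separately. The case report form is not among the documents, and parts of the PCWG3 table in Appendix 10 are missing from the text available. Either could provide for SSE collection.

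Finally, SAP Section 8 reports termination after 13 patients and no efficacy analysis. No SSE estimate from this trial will carry the bias. That lowers the priority but does not make the written rule sound.

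**Conclusion.** The point holds as a defect in the written rule. SAP 6.4.2 does not link SSE censoring to SSE ascertainment, and for at least some patients it extends follow-up past the date when disease-related SSEs stop being systematically captured. The direction is clear: the event-free rate is biased upward.

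The size is not established. The 7 to 31 points at 12 months is an illustration. It rests on assumed SSE rates, time on drug and survival borrowed from another study, independent exponential times, and censoring at the last follow-up contact. If last visit means the Safety Follow-up Visit, little bias remains. The documents do not support quoting any of these figures as the bias in this trial.

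Practical impact is low. The endpoint is secondary, single-arm and descriptive, and its analysis has been dropped.

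**What to change.** In SAP 6.4.2, censor patients without an SSE at the last date on which SSE status was ascertained, and define that date.

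If SSEs are not collected in long-term follow-up, censor no later than the earlier of 30 days after the last dose or the start of new anticancer therapy. A plain 30-day limit is not enough, because adverse event reporting can stop sooner. State also that this censoring may be informative: it follows stopping drug, often for progression, so it removes the misclassified time without guaranteeing an unbiased estimate.

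Where follow-up continues, or the text is reused in another protocol, add one dated SSE item to the existing visits and 12-weekly contacts in Appendix 1 and Section 5.6.2.

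The cost is a sentence or two in the SAP and, where collection is extended, one form item. No new visits are needed. For this trial's report nothing has to be re-run.
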